7.4 Duration of Therapy

Subjects must be withdrawn from the study treatment for the following reasons:

Patients are expected to receive one neo-adjuvant dose of Radium-223 followed by EBRT for 2 to 6 weeks followed by 5 additional cycles of Radium-223. The treatment phase of the study should be completed in approximately 6 months pending dose delay or discontinuation

- Subject withdraws consent from the study treatment and/or study procedures. A subject must be removed from the trial at his/her own request or at the request of his/her legally acceptable representative. At any time during the trial and without giving reasons, a subject may decline to participate further. The subject will not suffer any disadvantage as a result.
- Subject is lost to follow-up.
- Death.
- Disease progression as defined in section 10

- In the event of disease progression, the subject will no longer receive study treatment, but will remain on the study for all follow-up evaluations, which include indicated imaging studies, lab draws, and all questionnaires.

Subjects may be withdrawn from the study for the following reasons:

- The subject is non-compliant with study drug, trial procedures, or both; including the use of anti-cancer therapy not prescribed by the study protocol.
- If, in the investigator's opinion, continuation of the trial would be harmful to the subject's well-being.
- The development of a second cancer.
- Development of an intercurrent illness or situation which would, in the judgment of the investigator, significantly affect assessments of clinical status and trial endpoints.
- Deterioration of ECOG performance status to 4.

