10.1 Primary Endpoint – 15 month Hormone Free Survival

The primary objective is to determine the hormone-therapy-free survival time for men treated with sequential EBRT and Radium-223 and determine whether it is a 20% risk reduction over the institutional comparator of 100% use of systemic therapy by 15 months. The primary outcome is 15 months hormone-free survival. Patients will remain on study treatment for the duration defined by the calendar or for disease progression. Patients will be followed up to determine the start of ADT which will be used to measure the primary end point.

For the purposes of this study, progression will be measured after the completion of EBRT and the delivery of Cycle 2 of Radium-223 and defined as either:

Biochemical Progression:

- For those subjects whose PSA is greater than 20ng/ml at baseline who do not have any PSA decrease after starting therapy: biochemical progression will be defined as a 10% rise over the baseline.

- For those subjects whose PSA is greater than 20ng/ml at baseline, who demonstrate decrease in PSA after study treatment: if the PSA nadir remains > 20ng/ml, biochemical progression will be defined as a PSA rise greater than 10% of the PSA nadir. If the PSA nadir is < 20ng/ml, biochemical progression will be defined as a PSA rise greater than 10% of the PSA nadir.

-For those subjects whose PSA is less than 20ng/ml at baseline: biochemical progression will be defined as PSA >20ng/ml and 10%.

*Any PSA test that would meet a failure definition has to be validated through Huntsman Cancer Institute or a Veterans Affairs Hospital with a repeat PSA test no sooner than 5 days and no later than 14 days from the initial notification of the result demonstrating progression.

OR

Radiographic progression: Any new, progressing, or reappearing lesion on Bone Scan, CT/Scan, or MRI compared to the same scan performed previously. Radiographic Progression will be determined by Prostate Cancer Clinical Trials Working Group (PCWG2) and RECIST 1.1 as described below (section 10.1.1).

* Of note: For a patient to meet radiographic progression criterion for appearance of new bone lesion only, the patient must demonstrate appearance of new bone disease, as confirmed by the treating radiation oncologist, and also meet the biochemical progression definition set out above.

OR

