Clinical Progression: the development of any skeletal related event defined as: time to any EBRT not required as a study procedure, time to first pathological bone fracture, time to spinal cord compression, or time to surgical intervention.

RECIST 1.1 and PCG 2 Assessments:

The following definitions and criteria for RECIST 1.1 and PCWG2 should be used for the baseline evaluations of existing disease and for the ongoing evaluation of tumor responses.

Measurable lesions - lesions that can be accurately measured in at least one dimension with longest diameter (LD) ≥ 10 mm using CT, MRI, or caliper measurements or ≥ 20 mm with x-ray.

Non-measurable lesions - all other lesions including small lesions (LD < 10 mm with CT, MRI, or caliper measurements or < 20 mm with x-ray).

Documentation of “Target” and “Non-Target” Lesions

- All measurable lesions up to a maximum of two lesions per organ and five lesions in total, representative of all involved organs should be identified as ***target lesions*** and recorded and measured at baseline.
- Target lesions should be selected on the basis of their size (lesions with the longest diameter) and their suitability for accurate repeated measurements (either by imaging techniques or clinical assessments).
- A sum of the LD for *all target lesions* will be calculated and reported as the baseline sum LD. The baseline sum LD will be used as the reference by which to characterize the objective tumor response.
- All other lesions (or sites of disease) should be identified as ***non-target lesions*** and should also be recorded at baseline. Measurements of these lesions are not required, but the presence or absence of each should be noted throughout follow-up.

RECIST Response Criteria

Evaluation of target lesions	
Complete Response (CR)	Disappearance of all target lesions (Must persist for a minimum of four weeks)
Partial Response (PR)	At least a 30% decrease in the sum of the LD of target lesions, taking as reference the baseline sum LD (Must persist for a minimum of four weeks)
Progressive Disease (PD)	At least a 20% increase in the sum of the LD of target lesions, taking as reference the smallest sum LD recorded since the treatment started or the appearance of one or more new lesions
Stable Disease (SD)	Neither sufficient shrinkage to qualify for PR nor sufficient increase to qualify for PD, taking as reference the smallest sum LD since the treatment started

Evaluation of non-target lesions	

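### Section 8.1.1 both forbids and permits further radium after a pathological fracture or cord compression, leaving up to 4 of 6 doses undetermined

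*Combined protocol and SAP*

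**What the plan says.** **Stopping.** Section 7.4 lists progression, as defined in section 10, among the mandatory reasons to leave study treatment, and adds: "In the event of disease progression, the subject will no longer receive study treatment". Under its disease-progression heading, section 8.1.1 likewise makes stopping compulsory for radiographic, clinical or confirmed biochemical progression.

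**What counts.** Section 10.1 states that "progression will be measured after the completion of EBRT and the delivery of Cycle 2 of Radium-223". Clinical progression is any skeletal event: EBRT outside the study, or "time to first pathological bone fracture, time to spinal cord compression, or time to surgical intervention".

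**Continuing.** Later subheadings of section 8.1.1 point the other way. After cord compression in the treatment period, radium may be given again once the man has recovered sufficiently. After a pathological fracture, treatment may go ahead on schedule, and the same paragraph names progressive disease as one possible cause. If surgery is needed, treatment should go on where the investigator thinks it safe.

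**Evaluability.** Section 10 calls a man evaluable after cycle 1, EBRT and at least 3 radium cycles. Section 11 bases its power and its 2-of-20 rule on 20 evaluable men, but plans the primary report at 15 months for everyone enrolled.

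**Two further rules in section 10.1.** For a baseline PSA above 20 ng/ml that falls, "if the PSA nadir remains > 20ng/ml, biochemical progression will be defined as a PSA rise greater than 10% of the PSA nadir"; the companion sentence reads "If the PSA nadir is < 20ng/ml, biochemical progression will be defined as a PSA rise greater than 10% of the PSA nadir". For a baseline below 20, "biochemical progression will be defined as PSA >20ng/ml and 10" per cent. A note on radiographic progression says that "For a patient to meet radiographic progression criterion for appearance of new bone lesion only", the man must show new bone disease "and also meet the biochemical progression definition set out above".

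**The concern.** From cycle 2 onwards, a fracture or cord compression falls under two instructions that cannot both govern. Two investigators, each following the text, could give the same man different amounts of a radioactive drug. That is a safety and conduct problem first.

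It also reaches the analysis. The number of radium cycles decides who is evaluable, so the choice of sentence can decide whether an early-progressing man counts in the primary result. If such men left the denominator, the proportion free of systemic therapy would tend to look better than it is.

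**Working it through.** **Step 1: the plan's own figure.** Inputs from section 11: n = 20, reject if 2 or more men are free of systemic therapy, 1% free under the null, 20% free under the alternative.

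- Power = 1 − 0.8^20 − 20 × 0.2 × 0.8^19 = 1 − 0.01153 − 0.05765 = 0.931. This agrees with the stated 93%.
- One-sided error = 1 − 0.99^20 − 20 × 0.01 × 0.99^19 = 1 − 0.81791 − 0.16523 = 0.017, below 0.05.

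Progression enters neither formula. Both assume that 20 men are analysed.

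**Step 2: the instructions side by side, for an event after EBRT and cycle 2.**

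| Event | Clinical progression (10.1)? | General rule (7.4, 8.1.1) | Specific text in 8.1.1 | Conflict |
|---|---|---|---|---|
| Pathological fracture | yes | stop | may continue | yes |
| Cord compression | yes | stop | may resume on recovery | yes |
| Surgery | yes | stop | should continue if safe | only if the text covers skeletal surgery |
| EBRT outside the study | yes | stop | no contrary text | no |

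Two of the four event types conflict outright and a third does so on one reading. Before EBRT and cycle 2 are complete, progression is not yet measured, so there is no conflict.

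**Step 3: doses at stake.** Remaining doses = 6 − last cycle given.

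- After cycle 2: 4
- After cycle 3: 3
- After cycle 4: 2
- After cycle 5: 1

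Cycles are 28 to 42 days apart (section 8.1.1; Study Calendar, footnote 11). Cycles 2 to 6 therefore span 4 × 28 = 112 to 4 × 42 = 168 days. The upper figure is not firm, because section 8.1.1 also allows 6 to 8 weeks after a dose for blood counts to recover.

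**Step 4: evaluability.** If section 10 means 3 cycles in total, a man stopped after cycle 2 is not evaluable. If it means 3 cycles on top of cycle 1, that is 4 in total, and a man stopped after cycle 3 also fails. Continuing could make either man evaluable.

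**Step 5: the two lesser rules.** Both nadir branches reduce to PSA > 1.1 × nadir, so the split changes no result. Below a nadir of 20/1.1 = 18.2 ng/ml, progression is reached while PSA is still under 20. With a nadir of 2, for example, the threshold is 2.2. A man with baseline below 20 cannot progress biochemically until PSA exceeds 20.

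For new bone lesions, write B for biochemical progression and N for new bone lesions only. Under the note, the criterion is B or (N and B), which equals B. So N never adds an event. Under the PCWG2 bone-scan rule later in section 10.1 (2 or more new lesions, no PSA condition), N would add one for a man who meets no other criterion.

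**The case against.** The best defence is that the texts can be reconciled. Progression is measured only after EBRT and cycle 2, so the permissive wording has a genuine place before then. For fracture and cord compression it says only that treatment may go on, whereas the general rule is mandatory, so an investigator who stops breaches neither. At a single site, this may amount to a missing cross-reference.

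The early period is indeed a real domain for that wording, and the fix below uses it. But section 8.1.1 does not state the limit. Its cord-compression text refers to the treatment period as a whole, and its fracture text permits treatment even after naming progressive disease as a cause. The reconciliation therefore has to be supplied by the reader.

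Three stronger readings may tempt a reader:

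- **The primary test is undermined.** The documents do not support this, because the endpoint is the start of systemic therapy, not progression. Nor is the endpoint wholly insulated, given the evaluability rule.
- **The bone-lesion note is an error, and the PCWG2 rule should be the main count.** The note is an explicit qualification of PCWG2, and it does have an effect: it removes new bone lesions alone as a trigger. It also reaches no analysis specified in section 11, whose only progression-free survival analysis is exploratory and uses biochemical or clinical progression.
- **The duplicated nadir branches misdirect dosing.** As written they give one workable rule, and the documents do not show that a different one was intended.

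**Conclusion.** The contradiction over fracture and cord compression is real and should be fixed. It leaves 4, 3, 2 or 1 of 6 radium doses undetermined for an event after cycle 2, 3, 4 or 5. The surgery conflict is conditional on that text covering skeletal surgery, and EBRT outside the study raises none.

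The power of 0.931 with 20 men stands. What is open is whether men stopped early remain among those 20: section 10 would call some of them non-evaluable, while section 11 speaks of all enrollees.

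The dose counts assume the six-cycle schedule. The documents do not allow an estimate of how many men would have such an event. The nadir branches and the bone-lesion note are secondary wording points only.

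**What to change.** **Main change (section 8.1.1).** Limit the fracture and cord-compression continuation text to events before EBRT and cycle 2 are complete, and require stopping afterwards. Say that the surgery text means non-skeletal surgery.

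**With it (sections 10 and 11).** State that men stopped for progression stay in the 15-month primary denominator, whatever number of cycles they received. Section 7.4 already keeps them in follow-up, so the outcome can still be observed.

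**Cost.** It takes one wording amendment. Some men would receive up to 4 fewer doses than the permissive text allows. Without the denominator statement, a man stopped after cycle 2 (or after cycle 3, on the stricter reading of section 10) would be non-evaluable. The sample size and power figure stay as they are.

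**Secondary.** The sponsor should confirm the criterion for a nadir below 20; if the present one is intended, the split can go without changing any result. The bone-lesion note can stay. At most, add a sensitivity analysis of progression-free survival, which the Study Summary lists as a secondary objective, using the PCWG2 bone-scan rule. Bone scans are already in the calendar, so it needs no new ones. Its dates would be approximate, because the bone-scan footnote sets no interval for scans in follow-up.

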1.3 Exploratory Objectives

1.3.1 Evaluate whether a commercially available cell-cycle progression gene assay (Myriad CCP) performed on the original prostate biopsy or surgical pathology specimen correlates with biochemical or clinical progression free survival in the study population.

1.3.2 Evaluate whether a commercially available homologous recombination DNA repair assay correlates with biochemical or clinical progression free survival in the study population (Myriad HRD).

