showed a further improvement in overall survival to 3.6 months with a hazard ratio of 0.695 (i.e., 30.5% reduction in risk of death) [9]. Moreover, the toxicity profile appeared excellent with grades 3-4 neutropenia in 1.8% and thrombocytopenia in 4% of patients. Reassuringly, long-term, 24-month outcomes in the previous randomized phase II trial showed no increase in hematologic toxicities [6, 7].

Radiotherapy for Oligometastasis: In 1995, Hellman and Weichselbaum coined the term “oligometastases” to characterize a state of limited metastasis in which aggressive local control measures could be potentially curative [10, 11]. This led to the development of prospective clinical trials employing the use of Stereotactic Body Radiotherapy (SBRT) to ablate visible oligometastatic disease with curative intent [12]. This approach has been demonstrated to be safe and effective, with local control rates in the 80% range, and durable progression-free survival rates around 20%. In one of the only trials evaluating the role of SBRT exclusively in 40 patients with bone only metastatic prostate cancer, the actuarial 24-month local tumor control rate was 95.5% as measured by MRI and PET CT imaging and the median initial PSA before treatment was 5.4 ng/dl which dropped to 2.7 ng/dl after 3 months [13]. We propose that the combination of external beam radiotherapy and Radium-223 will be an effective therapy at controlling oligometastatic prostate cancer in hormone-therapy naïve patients.

Comparator Cohort:

At the Huntsman Cancer Institute at the University of Utah, 100% of persons have been started on systemic therapies to treat their metastatic prostate cancer by 15 months of the identification of oligometastasis. The goal of the current study is to assess whether the Radium-223 and EBRT to oligometastatic sites will delay the need to initiate additional antineoplastic systemic therapies by 15 months.

Other Comparators of interest that are not specified as the primary aim:

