- Time to first SRE (defined as time to EBRT, time to first pathological bone fracture, time to spinal cord compression and time to surgical intervention) was statistically significantly longer in the Radium-223 chloride group compared to placebo (median number of months=15.6 for Radium-223 chloride versus 9.8 months for placebo (HR=0.658, 95 CI 0.522–0.830, p= 0.00037).
- Time to total ALP progression (defined as $\geq 25\%$ increase compared to baseline/nadir) was statistically significantly longer in the Radium-223 chloride group 7.4 months compared to placebo 3.8 months (HR = 0.167, 95% CI 0.129 – 0.217; p= <0.00001).
- Time to PSA progression (defined as a $\geq 25\%$ increase and an increase in absolute value of ≥ 2 ng/mL compared to baseline/nadir) was also significantly prolonged in patients receiving Radium Ra-223 dichloride compared to patients receiving placebo (HR = 0.643, 95% CI 0.539,0.768; p = <0.00001)
- A total ALP response (defined as a confirmed $\geq 30\%$ or $\geq 50\%$ reduction compared to baseline) at week 12 was observed in higher proportions of subjects who were treated with Radium-223 chloride group (47% and 3% respectively) compared to those in the placebo (3% and <1% respectively) group.
- Subgroup survival analysis showed a consistent survival benefit for treatment with Radium Ra-223 dichloride, independent of total alkaline phosphatase (ALP), current use of bisphosphonates, prior use of docetaxel and baseline ECOG status. The results from the phase III ALSYMPCA study regarding time to external beam radiation therapy (EBRT) for pain relief and fewer patients reporting bone pain as

an adverse event in the Radium Ra-223 dichloride group indicate a positive effect on bone pain.

The most common adverse reactions ($\geq 10\%$) in patients receiving Radium Ra-223 dichloride were nausea, diarrhea, vomiting, and peripheral edema (Table 2.1). Grade 3 and 4 adverse events were reported among 57% of Radium Ra-223 dichloride-treated patients and 63% of placebo treated patients. The most common hematologic laboratory abnormalities in Radium Ra-223 dichloride-treated patients ($\geq 10\%$) were anemia, lymphocytopenia, leukopenia, thrombocytopenia, and neutropenia (Table 2.2). Treatment discontinuations due to adverse events occurred in 17% of patients who received Radium Ra-223 dichloride and 21% of patients who received placebo.

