5.1 Inclusion Criteria

Yes/No (Response of "no" = patient ineligible)

5.1.1 _____ Asymptomatic or symptomatic hormone naïve men with testosterone levels ≥ 100 ng/dL with previously treated localized prostate cancer who now have rising PSAs and five or fewer bone metastases.

5.1.2 _____ Subjects who have been previously treated with definitive and/or adjuvant/salvage radiotherapy to the primary site and/or regional lymph nodes with concurrent ADT are allowed if the last hormone therapy delivered > 6 months prior. Subjects who have had more than 30 days and fewer than 45 days of bicalutamide monotherapy for any reason within the 6 months prior to enrollment are eligible for the study, providing they have been off of the drug for at least 30 days prior to enrollment. Subjects who have had fewer than 30 days of bicalutamide are eligible for the study, as long as they discontinue the drug at least 5 days prior to the first study treatment.

5.1.3 _____ Histologic confirmation of Prostate Adenocarcinoma diagnosis.

5.1.4 _____ Age ≥ 18 years.

5.1.5 _____ Life expectancy of at least 2 years.

5.1.6 _____ Acceptable hematology and serum biochemistry screening values:

- White Blood Cell Count (WBC) $\geq 3,000/\text{mm}^3$
- Absolute Neutrophil Count (ANC) $\geq 1,500/\text{mm}^3$
- Platelet (PLT) count $\geq 100,000/\text{mm}^3$
- Hemoglobin (HGB) $\geq 10 \text{ g/dL}$
- Total bilirubin level $\leq 1.5 \times$ institutional upper limit of normal (ULN)
- Aspartate aminotransferase (AST) and alanine aminotransferase (ALT) $\leq 2.5 \times$ ULN
- Creatinine $\leq 1.5 \times$ ULN
- Albumin $> 2.5 \text{ mg/dL}$

5.1.7 _____ Willing and able to comply with the protocol, including follow-up visits and examinations.

5.1.8 _____ Karnofsky Performance Score >60 or ECOG equivalent.

5.1.9 Radiographic confirmation of oligometastatic diagnosis via Bone Scan validated by either CT scan, or MRI or PET/CT with Fluciclovine within the past 90 days.

5.1.10 Subjects who have not had surgical removal of their prostate and have a partner of child bearing potential must agree to use condoms beginning at the signing of the ICF until at least 6 months after the last dose of study drug. Because of the potential side effect on spermatogenesis associated with radiation, female partners of childbearing potential must agree to use a highly effective contraceptive method during and for 6 months after completing treatment.

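### Section 10.1 applies two very different PSA rules either side of a baseline of 20 ng/mL, so time to biochemical progression depends heavily on baseline PSA as well as on treatment

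*Combined protocol and SAP*

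**What the plan says.** Section 10.1 splits biochemical progression by baseline PSA:

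- Baseline above 20, PSA never falls: "biochemical progression will be defined as a 10% rise over the baseline".
- Baseline above 20, PSA falls: there is one branch for a nadir above 20 and one for a nadir below 20, but both carry the same rule. The second reads "If the PSA nadir is < 20ng/ml, biochemical progression will be defined as a PSA rise greater than 10% of the PSA nadir".
- Baseline below 20: "For those subjects whose PSA is less than 20ng/ml at baseline: biochemical progression will be defined as PSA >20ng/ml and 10". A percent sign follows and the sentence ends, so the value from which the 10% is measured is not given.

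A baseline of exactly 20 has no rule. A qualifying PSA must be confirmed by a repeat test at 5 to 14 days, and progression is assessed only after EBRT and Cycle 2.

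The same section counts a new bone lesion on its own as radiographic progression only if the biochemical definition is also met. Other radiographic progression and skeletal events are separate routes. On the primary endpoint it says: "Patients will be followed up to determine the start of ADT which will be used to measure the primary end point".

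Section 5.1 admits men "who now have rising PSAs and five or fewer bone metastases" and sets no PSA range. The only PSA level given for men treated in a similar way is in Section 2, from a cited SBRT study of 40 men with bone-only disease: "the median initial PSA before treatment was 5.4 ng/dl which dropped to 2.7 ng/dl after 3 months".

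The Study Summary lists progression-free survival (PFS) as a secondary objective. Section 1.3 asks whether each of the CCP and HRD assays "correlates with biochemical or clinical progression free survival in the study population". Section 11 plans exploratory Cox models for correlations with survival endpoints.

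**The concern.** The event definition changes abruptly at a baseline characteristic. Below 20, a man must reach a fixed level that may be several times his own nadir. Above 20, he needs only a small relative rise, with no floor. Two men with the same nadir and the same regrowth can therefore have very different times to biochemical progression.

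Because new-bone-lesion-only progression needs the same PSA criterion, imaging does not fully compensate: a man who started below 20 and develops only new bone lesions is not counted until his PSA passes 20.

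With about 20 men, PFS will partly reflect the mix of baseline PSA values. A marker related to baseline PSA could also appear to predict progression, or fail to, because of the definition.

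**Working it through.** The plan gives no figure for biochemical progression, so there is none to reproduce. Its 93% power for the primary test does reproduce: 1 − 0.8^20 − 20 × 0.2 × 0.8^19 = 1 − 0.0115 − 0.0576 = 0.931. That calculation does not use the PSA rule.

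**Inputs.** The thresholds are from Section 10.1. The medians 5.4 and 2.7 at 3 months are from Section 2. They are printed in ng/dl and taken here as ng/mL; read literally they would be 100 times smaller and the gap to 20 wider. PSA is assumed to grow exponentially with doubling times of 3, 6 or 12 months, because the documents give none.

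**Formula.** Doublings needed = log2(threshold / starting value). Time = doublings × doubling time.

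**1. The jump at 20.** Take two men, both with a nadir of 5.
- Started at 21: threshold 1.1 × 5 = 5.5; log2(1.1) = 0.1375 doublings.
- Started at 19: threshold 20; log2(20/5) = 2.00 doublings.

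**2. The missing reference for the 10%.** For the man who started at 19, the threshold is 20 if the 10% is over nadir (5.5 does not bind), 1.1 × 19 = 20.9 if over baseline, and 1.1 × 20 = 22 if over 20. At a 6-month doubling time these take 12.0, 12.4 and 12.8 months from nadir. The gap in the wording matters much less than the jump.

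**3. The cited medians, as illustration.** 20/5.4 = 3.7-fold (1.89 doublings); 20/2.7 = 7.4-fold (2.89 doublings).

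| Case | 3-month doubling | 6-month | 12-month |
|---|---|---|---|
| Started at 21, nadir 5: months after nadir | 0.4 | 0.8 | 1.7 |
| Started at 19, nadir 5: months after nadir | 6.0 | 12.0 | 24.0 |
| Baseline 5.4, no PSA fall: study month | 5.7 | 11.3 | 22.7 |
| Baseline 5.4, falls to 2.7 at month 3: study month (3 + 2.89 × doubling time) | 11.7 | 20.3 | 37.7 |

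The man in the last row crosses by month 15 only if his doubling time is below 12/2.89 = 4.2 months, and within two years only if it is below 21/2.89 = 7.3 months.

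**4. Dependence on baseline.** With a 6-month doubling time and no PSA fall, a man crosses 20 at 25.9 months from a baseline of 1, 11.3 from 5.4, 6.0 from 10 and 2.5 from 15. A man above 20 meets his 10% rule at 0.8 months, before assessment is allowed to begin.

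**5. One rule for all.** Section 3.1.4 quotes a definition requiring a rise of at least 25% and at least 2 ng/mL over baseline or nadir. From a nadir of 5 the threshold is max(6.25, 7) = 7 for both men: log2(7/5) = 0.485 doublings, or 2.9 months at a 6-month doubling time.

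**The case against.** **Treatment still matters.** A reader might infer that PSA progression is set by baseline PSA rather than by treatment. The documents do not support that. Under the same rule, halving PSA at month 3 moves the illustrative man from month 11.3 to month 20.3, so his late crossing is partly a treatment response. This stands: baseline is a strong influence alongside treatment and growth rate.

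**The population is not known.** A reader might also infer that most men in this trial will start near 5.4. Those are medians from a cited study, which the protocol does not describe as hormone-naïve, and no PSA distribution is stated for this trial. This stands; the figures only illustrate.

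**Observed differences will be smaller.** On thresholds alone, 2.89 against 0.1375 doublings is 21-fold. With PSA every 3 months in follow-up, crossings at 17.3 and 0.8 months after nadir would be seen at about 18 and 3 months, roughly 6-fold. This stands, but 6-fold is still large.

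**The reach is limited.** The primary endpoint is measured by ADT start. PFS is absent from Section 1.2 and has no analysis in Section 11. The correlative assays are optional, and Section 11 names only CCP. Section 1.2.4 already has a PSA measure without the cut at 20, the time for PSA to double from baseline. All this limits the importance of the point; it does not remove the discontinuity from PFS.

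**It may be a drafting fault.** Two nadir branches with identical wording suggest that one was meant to differ. That is likely enough to make reconciliation the first request.

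**A uniform rule is not perfectly uniform.** The quoted definition comes from a castration-resistant trial. Section 8.1 stops study treatment on confirmed Section 10.1 progression, so later treatment will still differ by baseline group. This is why it belongs in a sensitivity analysis.

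**Conclusion.** The definition is discontinuous at 20 and incomplete as printed. With a nadir of 5, the threshold is 5.5 or 20 depending only on whether the man started at 21 or 19; this needs no assumption about growth. Times in months rest on assumed exponential growth and assumed doubling times, and the 3.7-fold and 7.4-fold figures also rest on a cited study's medians and on reading ng/dl as ng/mL.

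The point bears on PFS and the exploratory biochemical PFS correlations. A reader might infer that the primary result is biased, since Section 1.1 speaks of ADT required for progression and Section 2 describes no PSA rule for the institutional comparator. The documents do not support more than a possible indirect effect: the endpoint is ADT start, and nothing shows how closely ADT start would follow the PSA rule. Its size cannot be computed.

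**What to change.** 1. **Section 10.1:** reconcile the PSA definitions. These are the two nadir branches with the same rule, the missing reference for the 10%, the unassigned baseline of exactly 20, and the jump at 20. The choice of any rule that governs study treatment is for the sponsor's clinicians.

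2. **Section 11, analysis only:** add a sensitivity version of PFS and of the CCP and HRD Cox models, using one PSA progression rule for every man regardless of baseline and reported beside the Section 10.1 version. The definition quoted in Section 3.1.4 is one candidate, with its castration-resistant origin noted. Count start of ADT or other systemic therapy before the uniform rule is met as an event, and censor at that start in a second run.

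3. **Section 11:** report PFS descriptively by baseline PSA below and above 20.

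**Cost.** A few sentences, plus the programming of a second PFS derivation and its two runs. No new visits or samples are needed: PSA is already scheduled at each cycle and in follow-up, and Section 7.4 keeps men on study for laboratory tests after progression. The drawbacks are two PFS versions to explain, subgroups that will be small in a 20-man trial, and some remaining dependence on baseline through treatment stopped under Section 10.1.
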